#### 6.3 Assessments

#### **Data collection**

The study duration will be until 12 weeks  $\pm$  1 week postoperatively. Data will be collected (1) 4 weeks preoperatively, (2) prior to hospital admission for TKA, and (3) at 3, 6, and 12 weeks postoperatively (see table in 1.4). All data will be entered and maintained in REDCap, an electronic data capture tools hosted at Cleveland Clinic [20].REDCap (Research Electronic Data Capture) is a secure, web-based application designed to support data capture for research studies, providing 1) an intuitive interface for validated data entry; 2) audit trails for tracking data manipulation and export procedures; 3) automated export procedures for seamless data downloads to common statistical packages; and 4) procedures for importing data from external sources. Only members of the study team (i.e. the personnel listed on the IRB application) will have access to protected health information of patients included in this study.

The following will be collected on all patients in the study and managed using REDCap:

- 1 MRN
- 2. Name
- 3. Date of birth
- 4. Address
- 5. Phone number
- 6. Email address
- 7. Date of surgery
- 8. Visit dates
- 9. Age at the time of surgery
- 10. Gender: male or female
- 11 BMI
- 12. Comorbidities
- 13. Date of surgery: (month/day/year)
- 14. Any complications (e.g., emergency department visits, infection, reoperation, etc.)
- 15. KOOS, VR-12, and VAS pain questionnaire forms

# **Pretreatment Assessments**

Before treatment, the following assessments/tests will be performed and the results will be recorded on the appropriate pages of the CRF, and or Microsoft excel, Microsoft Word, and REDCap:

- Eligibility criteria, including written informed consent
- Age, gender, height/weight/BMI
- Concomitant diseases
- Physical examination
- Baseline range of motion of affected knee
- Baseline timed up and go test (TUG test, detailed in Appendix A and as described by Podsiadlo et al.)

- Baseline Stair Climb test
- Baseline QFM strength
- Baseline Modified KOOS and VR-12 assessments
- Baseline VAS pain score
- Current medications
- Any use of ambulation assist device

# **Presurgery Assessments**

Before surgery, the following assessments/tests will be performed and the results will be recorded on the appropriate pages of the CRF, and or Microsoft excel, Microsoft Word, and REDCap:

- Device usage patterns (thru app for preop NMES group)
- Range of motion of affected knee
- TUG test
- Stair Climb test
- QFM strength
- Modified KOOS and VR-12 assessments
- VAS pain score
- Current medications
- Activity levels using Misfit Wearables® fitness monitor will be uploaded and incorporated into online app

# **Operative Assessments**

The following will be collected from the Operative and Anesthesia Records and recorded on the appropriate pages of the CRF, and or Microsoft excel, Microsoft Word, and REDCap:

- Surgeon name
- Approach used
- Randomization assignment
- Diagnosis
- Length of surgery
- Estimated blood loss
- Type of anesthesia
- Implant type

#### **Postoperative Assessments**

After surgery, one or more of the following will be collected through the online app and at follow-up visits.

- Device usage patterns (thru app)
- Range of motion of affected knee (thru app and at follow-up)
- TUG test
- Stair Climb test
- QFM strength
- Modified KOOS and VR-12 assessments
- VAS pain score

- Length of stay (hospital, extended care facility)
- 90 day readmission rate
- Discharge Disposition (home vs skilled nursing facility vs inpatient rehabilitation)
- Patient Satisfaction measures
- Any use of an ambulation assist aid
- Activity levels using Misfit Wearables® fitness monitor will be uploaded and incorporated into online app

# The NMES device application will not collect any PHI.

First and last name: will not be included, rather a study ID number. The key will be kept in secure location by research coordinator.

Email: not included

PIN: random number generated

Height, weight, gender: Ok for device app to collect

Date of birth: All study participates will be given a random date of 1/1/2015 Type of surgery: Total Knee arthroplasty Ok for device app to collect

Surgery location: anatomic location, knee

Date of surgery: All study participates will be given a random date of 1/1/2015

### Confidentiality of the data

All data will be anonymized by assigning study codes. The only document linking study codes to patients will be protected by a password and safely stored on a password protected desktop computer in a locked CCF office. Data obtained will only be shared with individuals who have an active CCF ID and identified as investigators or coordinators in this study protocol. The data will be stored using the intranet database REDCap, Microsoft Excel spreadsheet and Microsoft Word.

# 6.4 Withdrawal and Lost to Follow Up

Patients have the right to withdraw from the study at any time for any reason. The investigator, acting in the best interests of the patient, also has the right to withdraw patients from the study. Any patient requiring in-clinic NMES use more than 4 times during the 12 week follow-up period will be withdrawn from the study. In the event of early withdrawal, efforts will be made to complete and report the observations up to the time of withdrawal as thoroughly as possible. If the reason for removal of a patient from the study is an adverse event, the event will be recorded on the Complications/ Adverse Event Case Report Form. All efforts will be made to follow the patient until the condition resolves or the investigator determines that the patient's health has returned to an acceptable state.

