#### 1.3 Outcome Assessments

These three groups will be analyzed using several outcome measures including validated patient-reported outcome measures the Knee Injury and Osteoarthritis Outcome Score(KOOS) [1], and Veterans RAND 12 item health survey (VR-12))[2], knee active range of motion (extension, flexion), quadriceps femoris muscle (QFM) strength, the Timed Up and Go Test [3] and the Stair Climb Test. The primary endpoint for the study is QFM strength. However, of secondary interest will be: 1) other physical performance measures (i.e. limb symmetry index and gait speed, activity levels), 2) Visual Analogue Scale (VAS) pain levels [4], on outpatient follow-up and immediately before & after NMES therapy, 3) length of stay, 4) Patient dependence on assistive device, 5) Patient satisfaction measures, 6) Patient discharge disposition, 7) Patient readmission rate. The proprietary app for this product will be used to track device usage (intensity, duration of session, frequency of use), knee range of motion and gait speed.

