# Postoperative Care

Postoperative care will be standardized according to the protocol routinely used at our institution with rapid mobilization, gait training and range of motion [11]. Outpatient physical therapy will be scheduled as needed based on the therapist's assessment of recovery. Physical therapy locations must be Cleveland Clinic affiliated due to the need to use staff who have appropriate training on the NMES device usage to ensure accurate data collection. Pain will be controlled with orally administered long- and short-acting narcotics supplemented by parenteral narcotics as necessary. All study patients will receive standard of care anesthesia protocol.

Following discharge, patients will return for visits with a member of the research team at 3 weeks  $\pm$  7 days, 6 weeks  $\pm$  7 days, 12 weeks  $\pm$  7 days. Data will be collected and reported on the appropriate Case Report Forms at these follow-up visits.

As a last resort, if a patient is unable to keep one of these appointments, he/she will be either be mailed or emailed the OrthoMidas forms so the patient can fill them out. The patient will date and time the forms. They will then send the form back in a pre-addressed envelope. The patients email will be verified by the patient during a clinical visit to ensure accuracy of the correct recipient. Patients not responding to the initial mailer will be contacted by phone and forms may be administered over the phone. The mailers and/or phone calls will allow us to collect all data except the physical function measures. At the completion of the study, patients

will be given a voluntary survey about their experience with the clinical trial, which will be given in person, and or mail and email.

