### 7. CLINICAL OUTCOMES

# 7.1. Sample Size Justification

A recent review paper written by Maddocks et al looked at eight different studies that used quadriceps muscle strength as an outcome and created a pooled analysis. They found a standardized mean difference of 0.90 for quadriceps muscle strength between control and NMES intervention groups. Sample size was calculated using this standardized mean difference, along with 80% power and the level of significance (p-value) set to 0.05. This study will require 20 patients per group. However, adding in a 10% expected dropout rate, planned enrollment will be 22 patients per group for a total enrollment of 66 patients.

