# 7.2. Statistical Analysis

Data will be analyzed using intent-to-treat methodology (Herman et al JBJS 2009), utilizing the original treatment group to which a patient was assigned. Differences between means will be analyzed using Student's t-test, while categorical variables will be tested using frequency tabulations comparing outcomes between treatments with the Pearson chi-square test. Differences will be considered significant at the level of  $p \le 0.05$ .

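### Section 6.4 withdraws patients from the study after more than 4 in-clinic NMES uses, so later QFM strength is lost and the intent-to-treat analysis in section 7.2 cannot include them

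*Combined protocol and SAP*

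**What the plan says.** Section 6.4 (Withdrawal and Lost to Follow Up) contains a mandatory rule: "Any patient requiring in-clinic NMES use more than 4 times during the 12 week follow-up period will be withdrawn from the study". The removal is from the study, not only from treatment, and it applies in all three arms. For any early withdrawal, the section says that "efforts will be made to complete and report the observations up to the time of withdrawal". The only contact it describes after that point is for removals caused by an adverse event: "All efforts will be made to follow the patient until the condition resolves". That concerns the patient's health, not strength testing.

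Section 7.2 (Statistical Analysis) says "Data will be analyzed using intent-to-treat methodology", explained as "utilizing the original treatment group to which a patient was assigned". Means are compared with Student's t-test. Neither section 7.2 nor any other section names imputation, a repeated-measures model, a sensitivity analysis or a rule for patients without an outcome.

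Section 1.3 states: "The primary endpoint for the study is QFM strength". It names no primary time point. The schedule in section 1.4 measures quadriceps femoris muscle (QFM) strength before surgery and at 3, 6 and 12 weeks after it. Under Postoperative Care in section 6.2, the fallback for missed appointments is mail, email or telephone, and these contacts "calls will allow us to collect all data except the physical function measures". Section 7.1 allows for loss by "adding in a 10% expected dropout rate, planned enrollment will be 22 patients per group".

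**The concern.** The rule acts on an event that happens after randomisation, and the protocol itself imposes the resulting loss. It is therefore avoidable in a way that ordinary dropout is not. A patient who passes the count in week 5, for example, has a 3-week strength value but none at 6 or 12 weeks. A t-test leaves out anyone without a value, so the comparison at those visits no longer covers all the patients randomised.

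The trigger may also be related to the endpoint. Section 6.2 schedules outpatient therapy according to the therapist's view of recovery, and section 2 links NMES to quadriceps activation deficits. Need for clinic NMES could differ between arms with and without a home unit. If weaker patients are lost mainly from control, the benefit is understated; if mainly from an NMES arm, it is overstated. Strength that was never measured cannot be used afterwards to find out which happened.

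**Working it through.** **The texts side by side.** Section 6.4 ends study participation and provides for observations only to that point. Section 7.2 requires analysis by assigned arm. Values from before withdrawal can be analysed that way; later values do not exist. The remote fallback would not fill the gap even if it were extended to withdrawn patients, because it excludes physical function measures.

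**The plan's own sample size.** Inputs from section 7.1: standardised mean difference (SMD) 0.90, 80% power, significance level 0.05 (taken as two-sided).
- n per arm = 2(1.960 + 0.842)² / 0.90² = 19.4, so 20. This matches the plan.
- 20 × 1.10 = 22 per arm and 66 in total, also as planned.
- Power of the t-test (noncentral t) is 83.0% at 22 per arm and 79.2% at 20.

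**Loss of numbers alone.** The rates for the rule are assumed. Ordinary 10% dropout leaves 22 × 0.90 = 19.8 per arm, with power 78.8%. If the rule removes a further 5%, 10% or 20% of those enrolled, 18.7, 17.6 or 15.4 remain, with power 76.3%, 73.6% or 67.5%.

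**Selective loss.** Assumed: a recovery measure X that drives the trigger and strength Y are bivariate normal with SD 1 and correlation r. Only patients with X > c stay. With λ = φ(c) / (1 − Φ(c)), the mean of Y among those who stay rises by rλ, and its variance becomes 1 − r²λ(λ − c). The base is 22 per arm with no other dropout, and r = 0.7.

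*A. Same recovery threshold in both arms, with X and Y both shifted by 0.90 under NMES.* A fraction q of controls is removed.
- q = 10%: c = −1.282 and λ = 0.195 in control; c = −2.182 and λ = 0.0375 in NMES, where 1.5% are removed. Mean difference = 0.90 − 0.7(0.195 − 0.0375) = 0.790.
- q = 20%: c = −0.842 and λ = 0.350 in control; λ = 0.0913 in NMES, where 4.1% are removed. Mean difference = 0.90 − 0.7(0.350 − 0.0913) = 0.719.

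*B. Lowest fraction q on X removed from one NMES arm only.*
- q = 10%: mean difference = 0.90 + 0.7 × 0.195 = 1.036.
- q = 20%: mean difference = 0.90 + 0.7 × 0.350 = 1.145.

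*C. Loss unrelated to strength (r = 0), at the rates in A.* The difference stays at 0.90.

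| Case | Mean difference (change from 0.90) | Pooled SD | Observed SMD (change) | Power, or false-positive rate |
|---|---|---|---|---|
| No loss | 0.900 | 1.000 | 0.900 | power 83.0% |
| A, 10% | 0.790 (−12%) | 0.955 | 0.827 (−8%) | power 73.8% |
| A, 20% | 0.719 (−20%) | 0.929 | 0.774 (−14%) | power 64.6% |
| B, 10% | 1.036 (+15%) | 0.966 | 1.073 (+19%) | false positives 7.3% |
| B, 20% | 1.145 (+27%) | 0.954 | 1.200 (+33%) | false positives 12.3% |
| C, 10% | 0.900 | 1.000 | 0.900 | power 80.6% |
| C, 20% | 0.900 | 1.000 | 0.900 | power 77.5% |

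The false-positive rates apply when there is no true effect and the nominal two-sided level is 5%. Simulation with 40,000 trials per case gave power of 73.5% and 64.5% in A and false-positive rates of 7.1% and 11.7% in B.

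**Range.** Over r from 0.5 to 1.0 and 5% to 20% removed, the change in SMD runs from −4% to −16% in A and from +7% to +54% in B. The far ends need r = 1.0 and 20% removed. With r = 0.3 and 5% removed, the change is −2.6% in A and +4.1% in B, and the false-positive rate in B is 5.1%.

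**The case against.** Section 7.2 explains intent-to-treat only as analysis by assigned arm, so a withdrawn patient's earlier data can be analysed and both sections obeyed. Section 6.4 does not forbid later strength tests; that they are not done is an inference. The missing-data gap affects every dropout, not only these patients. No rate, reason or direction is given for the trigger, and 5% of an arm is about one patient. Removing 20% under this rule would be twice the planned dropout. Pattern B has no support in the documents, since the NMES arms already have home units. Limiting NMES outside the assigned regimen is also an understandable aim.

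The points on size stand: both magnitude and sign of any bias are unknown, and the figures are illustrations. The planned 20 evaluable patients already give only 79% power, so case C is close to plan. The SMD also reflects the shrunken SD, so the mean differences are the better guide for an analysis of means.

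The other points do not remove the problem. Non-collection is the natural reading of withdrawal from the study with data kept only to that time. Even on the narrow definition of intent-to-treat, these patients have no later outcome to analyse in their arm, and section 7.2 has no rule for them. If the aim is to limit contamination, recording the extra sessions serves it without losing the outcome.

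**Conclusion.** The concern holds and should be fixed. As written, section 6.4 removes randomised patients from later comparisons of the primary endpoint, while section 7.2 promises an intent-to-treat result and gives no method for the missing values. This rests on the text and on one inference, that no strength is measured after withdrawal.

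The size is conditional. With 10% to 20% removed and a correlation of 0.7, the mean difference of 0.90 could fall to between 0.79 and 0.72, or rise to between 1.04 and 1.15, depending on which arm loses patients. There is no bias if the loss is unrelated to strength, and almost no effect if in-clinic NMES is rare. Section 7.1 does not say whether its 2 extra patients per arm were meant to cover these withdrawals.

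**What to change.** Reconcile sections 6.4 and 7.2 by separating receipt of in-clinic NMES from leaving the study.

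- **Section 6.4:** record the number and dates of in-clinic NMES sessions as an intercurrent event or protocol deviation. Keep patients who pass the count at the 3, 6 and 12 week assessments unless they withdraw consent.
- **Section 7.2:** analyse these patients in their assigned arm and report how many there are in each arm. If a sensitivity analysis sets aside strength measured after the extra NMES, it should use a stated missing-data method, such as a mixed model for repeated measures or multiple imputation, and not a complete-case t-test.

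This concerns data collection and analysis only; no view is taken on who should receive in-clinic NMES or on the threshold. The cost is a short amendment and retention at visits already scheduled. The drawback is that some contamination stays in the comparison, which the stated intent-to-treat analysis already accepts.

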#### 6.5 Risks

On rare occasions, therapy can result in skin reactions such as rash, inflammation, irritation, or electrode burns. The risks associated with the routine aspects of the TKA procedure will be explained to the patient per the surgeon, anesthesiologist and hospital practice.

### 7. CLINICAL OUTCOMES

# 7.1. Sample Size Justification

A recent review paper written by Maddocks et al looked at eight different studies that used quadriceps muscle strength as an outcome and created a pooled analysis. They found a standardized mean difference of 0.90 for quadriceps muscle strength between control and NMES intervention groups. Sample size was calculated using this standardized mean difference, along with 80% power and the level of significance (p-value) set to 0.05. This study will require 20 patients per group. However, adding in a 10% expected dropout rate, planned enrollment will be 22 patients per group for a total enrollment of 66 patients.

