### 2. BACKGROUND

The current standard for rehabilitation after TKA consists of guided exercise therapy for up to 12 weeks after surgery. This includes inpatient, home, and outpatient therapy. The surgery and rehabilitation are highly successful at reducing or eliminating pain experienced preoperatively. However, QFM strength, overall function, and knee range of motion are often worse than preoperative levels for as long as 6 months after surgery and in some cases may persist for many years after that. Such quadriceps strength impairments after TKA have been largely attributed to voluntary activation deficits and can lead to a decrease in functional performance such as decreased gait speed, decreased balance which can lead to falls, and decreased stair climbing & chair rise abilities [5,6]

Since therapy alone does not adequately restore or improve upon the preoperative functional capabilities in a consistent and timely manner, it has been suggested that NMES used adjunctively with postoperative rehabilitation will alleviate the quadriceps muscle activation deficits. Early NMES use after TKA has been shown to: reduce knee extensor lag [7], increase walking speed [8], and improve QFM strength, knee range of motion, and function [5]. However, NMES initiated one month after TKA did not lead to improved QFM strength or function beyond the standard benefits gained from exercise alone [9], thus suggesting that the timing of NMES application after TKA is important.

It has previously been shown that preoperative QFM strength is predictive of postoperative function [10] but the benefit of prehabilitation remains in question [11–13]. To date, there has only been one pilot study assessing the benefits of NMES when initiated preoperatively[14]. This study only included 14 patients (9 NMES, 5 control) but was able to show that preoperative NMES usage may lead to greater QFM strength gains after TKA. Therefore, it will be important to assess the benefits of NMES both preoperatively and postoperatively in order to determine how it will be most beneficial to TKA patients.

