### 3. HYPOTHESIS AND SPECIFIC AIMS

**Study Hypothesis:** Our hypothesis is that use of the CyMedica e-viveTM NMES both preop and postop can improve functional outcomes following TKA.

**Specific Aim 1.** Test whether patients treated with preop and postop NMES show improved physical performance measures when compared to postop only NMES group and standard of care group.

**Specific Aim 2.** Test whether patients treated with preop and postop NMES show improved patient-reported outcomes when compared to postop only NMES group and standard of care group.

**Specific Aim 3.** Test whether patients treated with NMES require fewer outpatient physical therapy visits when compared to the standard of care group.

**Specific Aim 4.** Test whether patients treated with NMES have a decreased discharge disposition to extended care facilities as well as shorter length of stay in extended care facilities compared to standard of care group.

**Specific Aim 5**. Test whether patients treated with NMES have decreased 90 day postoperative readmission rates compared to the standard of care group.

**Specific Aim 6.** Test whether patients treated with NMES have decreased dependence of the use of ambulatory assist devices.

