# 4.2. Combined Treatment Group

This treatment group will be given the CyMedica Orthopedics e-vive system 4 weeks  $\pm$  7 days before day of scheduled surgery. The patients will begin using the unit until the day before surgery.

Patients will resume using the unit immediately following discharge (POD1 or POD2) + 7 days to take account of a bulky standard of care postoperative dressing, and continuing throughout the first 12 weeks postoperatively. During both preoperative and postoperative phases, patients will be instructed to use the device three times per day while doing activities, 20 minutes each session for 12 weeks.

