# 4.3 Postoperative only Treatment Group

This treatment group will be given the CyMedica Orthopedics e-vive system only upon discharge after surgery and will be asked to use the device as described in section 4.2.

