#### 5.4. Randomization

The patients will not be informed of their treatment assignment until a minimum of 4 weeks  $\pm$  7 days prior to day of surgery. A computer-based randomization generator (SAS, Inc.) will be used to assign patients into treatment arms in a 1:1:1 ratio, using a block randomization method. Patients in the combined treatment group will be given NMES units for device use beginning at at 4 weeks  $\pm$  7 days before surgery. Patients in the postoperative treatment only group will be given NMES units preoperatively and or upon discharge from the hospital. Those patients who are in the postoperative group only who receive the device preoperatively will be instructed to begin using the device only after their surgery. Patients in the control group will not receive any NMES units but will be given the option to crossover and receive a device at the end of the study.

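### Section 7.1's 80% power is derived from one control-versus-NMES effect size and does not extend to Aim 1's combined versus postop-only comparison at the postoperative visits

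*Combined protocol and SAP*

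**What the plan says.** Section 7.1 is the only sample-size text. Its single effect size comes from a pooled analysis of eight studies: "They found a standardized mean difference of 0.90 for quadriceps muscle strength between control and NMES intervention groups". Together with 80% power and a 0.05 level this gives 20 patients per group, raised to 22 per group and 66 in total for 10% dropout. The section does not say which pair of arms or which visit is powered, or whether the test is one- or two-sided.

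Section 1.3 makes quadriceps femoris muscle (QFM) strength the primary endpoint and names no primary visit. The schedule in section 1.4 has it measured at five time points, three of them after surgery ("at 3, 6, and 12 weeks postoperatively" in section 6.3).

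Aim 1 in section 3 asks whether combined preoperative and postoperative NMES patients "show improved physical performance measures when compared to postop only NMES group and standard of care group". That is two comparisons.

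Section 4.2 has the combined group resume the device after discharge, "continuing throughout the first 12 weeks postoperatively". Section 4.3 gives it to the other NMES group "only upon discharge after surgery and will be asked to use the device as described in section 4.2". Section 5.4 adds that postop-only patients who are handed the device early "will be instructed to begin using the device only after their surgery".

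Section 7.2 plans Student's t-tests for means, significant at 0.05 or below. It sets no order among comparisons or visits and no multiplicity rule.

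**The concern.** After surgery, combined versus postop-only is a comparison of two groups that both use NMES. It measures what preoperative use adds for patients who will have postoperative NMES in any case. A control-versus-NMES effect size does not supply a value for that increment. The background treats the question as a reason for the study ("it will be important to assess the benefits of NMES both preoperatively and postoperatively"), but the only preoperative NMES study it cites is a 14-patient pilot, for which it quotes no effect size.

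With an unqualified 80% in section 7.1, a reader of the results could assume that both parts of Aim 1 were powered alike. A non-significant combined-versus-postop-only result could then be taken as a sign that preoperative NMES adds nothing, when the data would be too imprecise to say so.

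There is a separate, smaller issue. Because no comparison or visit is ranked, the test that carries the 80% could be settled after results are known, and the false-positive risk over Aim 1's tests is not controlled.

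**Working it through.** **Inputs from the documents.** SMD 0.90, power 80%, level 0.05, 20 evaluable per group, 22 enrolled per group (section 7.1); two-sample t-test for means (section 7.2); 1:1:1 allocation (section 5.4).

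**Assumptions.** Two-sided testing, and a range of increments for combined versus postop-only. The documents state neither.

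**1. Reproduce the plan's figure.** Normal approximation, two-sided: n per group = 2 × (1.960 + 0.842)² / 0.90² = 15.70 / 0.81 = 19.38, so 20. Then 20 × 1.10 = 22, and 3 × 22 = 66. The plan's numbers are reproduced. A one-sided test would give 16. A Bonferroni allowance would give 24 for two tests and 26 for three. The stated 20 is therefore what one unadjusted, two-sided, two-group comparison requires.

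**2. Power by the planned t-test.** Noncentral t with 2n − 2 degrees of freedom and noncentrality d × √(n/2). For n = 20 there are 38 degrees of freedom, the critical value is 2.024 and the noncentrality is 3.162 × d. At d = 0.90 this is 2.846 and power is 79.2%.

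**3. Same calculation for combined versus postop-only at a postoperative visit.**

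| Assumed increment (SD) | Power, 20 per group | Power, 22 per group |
|---|---|---|
| 0.80 | 69% | 74% |
| 0.60 | 46% | 49% |
| 0.45 | 28% | 31% |
| 0.30 | 15% | 16% |

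The difference detectable with 80% power is 0.909 SD with 20 per group and 0.865 SD if all 22 are retained.

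**4. Precision.** The expected 95% CI half-width is 2.024 × √(2/20) = 0.640 SD (0.608 SD with 22 per group). An observed difference of zero would still be compatible with a benefit of up to about 0.64 SD.

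**5. Which visits are affected.** At 3, 6 and 12 weeks both arms have been told to use the device in the same way, so they differ by preoperative use. QFM strength is also measured at the presurgery visit (section 6.3: "Before surgery, the following assessments/tests will be performed"). By then only the combined group has used the device, so combined versus postop-only is NMES versus none. Steps 3 and 4 are therefore limited to the postoperative visits.

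**6. False positives over Aim 1's two comparisons.** With all three means equal, the two tests share the combined arm, so their statistics have correlation 0.5. The bivariate normal calculation gives 9.07% for at least one result below 0.05. Simulating 400,000 trials with 20 per arm gives 9.03%. This is for QFM strength at one visit; testing several visits raises it.

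**The case against.** Section 7.1 never says that its 80% covers only one comparison. That is an inference from the control-versus-NMES source and from the match to n = 20. A three-group ANOVA with means 0, 0.9 and 0.9 needs 19 per group, so it would fit almost as well. This stands as a caution on wording. Section 7.2 plans only t-tests for means, however, and that ANOVA pattern also has no difference between the two NMES arms, so it would not power the contrast either.

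It can also be said that no primary visit is named, and that at the presurgery visit 0.90 could be argued to apply to combined versus postop-only. That is correct. The point concerns postoperative visits only.

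Several stronger readings are tempting and are not supported:

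- *That the sample size is miscalculated.* It is not; the 20 reproduces.
- *That the trial has 28% power, or any other particular figure, for the added preoperative effect.* The documents give no increment, so each row of the table is an illustration.
- *That the plan assumes no difference between the NMES arms.* This would follow only if 0.90 were applied to both arms against control, and section 7.1 does not say that it is.
- *That 0.90 belongs to combined versus standard of care.* Section 7.1 does not say when the pooled studies gave NMES, or to which patients, so this cannot be verified.
- *That the plan intends to read a non-significant result as no benefit.* It says nothing of the kind; the risk lies in how readers might take the 80%.

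**Conclusion.** The point holds as one of scope. Section 7.1's calculation is sound for one comparison of an NMES group with standard of care on QFM strength at an SMD of 0.90 (79% by two-sided t-test). It does not extend to combined versus postop-only at 3, 6 or 12 weeks, for which the plan states neither effect size nor power. That contrast reaches 80% only if preoperative NMES adds about 0.91 SD, which is as large as the whole control-versus-NMES effect used for sizing. The absence of an assumed effect needs no assumption to establish. The 0.91 SD and the 0.64 SD half-width rest on two-sided testing and 20 evaluable patients per group.

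The missing ranking in section 7.2 is a separate gap that would remain whatever the power: about a 9% chance of at least one false positive over Aim 1's two QFM tests at one visit, and more over several. Both should be fixed before any results are seen. Neither calls for more patients.

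**What to change.** Keep the enrolment at 66.

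**Section 7.1.** Add text to this effect:

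> With about 20 evaluable patients per group, the study has approximately 80% power (79% by two-sided t-test at 0.05) for one comparison of an NMES group with standard of care on QFM strength at an SMD of 0.90. No effect size was assumed for combined versus postoperative-only NMES. At postoperative visits the difference detectable with 80% power for that comparison is about 0.91 SD, and the expected 95% CI half-width is 0.64 SD.

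**Section 7.2.** Before any results are seen, name one primary comparison on QFM strength at one visit:

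> The primary comparison is [combined NMES versus standard of care] on QFM strength at [one visit], tested at two-sided 0.05. The other two pairwise comparisons on QFM strength are secondary and will be reported as mean differences with 95% CIs. A non-significant difference between combined and postoperative-only NMES is not evidence of no preoperative benefit.

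Combined versus standard of care is suggested because it matches the study hypothesis. Postop-only versus standard of care then becomes secondary along with combined versus postop-only. The sponsor may choose another primary comparison if it justifies the effect size. If that is combined versus postop-only at a postoperative visit, the justified increment determines whether 66 is enough: 80% power needs 45 evaluable per group at 0.60 SD and 79 at 0.45 SD.

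**Section 3, Aim 1.** Any ranking sentence added here must be limited to QFM strength. Aim 1 covers all physical performance measures, and section 1.3 makes only QFM strength primary.

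**Cost.** A less favourable stated power, a commitment to one comparison, visit and two-sided test, and a lower rank for the comparisons not chosen. The last is a change of objective and not only of wording. With the suggested primary comparison, arms, visits and patient numbers do not change.
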